PROTOCOL: Apr 2014

Study Design: Phase I/II Clinical Trial (single arm)

Study participants: postnatal mothers and early neonates

Inclusion criteria

Postnatal mothers

Newborns with birth weight above 1.8 kg -- not sick and on full feeds

Testing device – RBM device. This is a

wearable sensor tag which can monitor temperature and transmit the data wirelessly using Bluetooth Low Energy.

The sensor tag operates off a CR2032 coin cell and can operate for 1 year. The enclosure package takes into account design elements

and incorporates hermetic sealing, no sharp corners, no crevices for accumulation of bacteria/dust and is easily sterilizable

(technical details of preliminary pre-clinical testing are available at URL:

http://chips.ece.iisc.ernet.in/images/2/25/BIODEVICES_2014_24.pdf.

Fig 1. Neonate in ICU with temperature probe

Fig 2. Neonate mannequin with RBM device

Fig 3. Baby-friendly enclosure

Fig 4. Disassembled prototype

[figure not shown]

Fig 5. Top and bottom view of the sensor

[figure not shown]
[figure not shown]

Fig 6. Vertical cross-sectional view of the enclosure

A gateway to bridge the sensor tag and the cellular infrastructure is housed independently or within a cellphone. The cellphone will display the temperature reading from the RBM device.

Location of device & probes

The RBM device will be placed on the abdomen between the xiphisternum and the umbilicus. Both the other probes (radiant warmer and the multichannel) will be placed near the RBM device separately.

Device adhesion

The RBM device will be strapped onto the abdomen using a combination of cotton and micropore adhesive tape.

Sample size and sampling technique

25 mother-baby pairs

250 readings (A sample size of about 250 readings will ensure a power of 80% to detect a 5% difference in measurements between devices with 95% confidence)

[At least 5 readings from mother and 5 readings from a neonate]

Pre-requisites for conduct of experiment

Radiant warmer and multichannel probe – both to be examined and serviced by the biomedical engineering dept; calibration certificate to be obtained from the responsible external agency

Testing comparisons

RBM device vs Radiant warmer probe vs Multichannel probe vs manual thermometer

Duration & frequency of sampling

Initially, after strapping on all 3 probes – there will be a waiting period of 10 minutes for temperature stabilization. Then the experiment will be started.

RBM device, multichannel probe & Radiant warmer probe – will automatically obtain readings continuously (every few seconds) and readings will be taken every 5 minutes.

Manual thermometer readings will be taken every 15 minutes at the following 5 timings: 0, 15, 30, 45 and 60 minutes

Participant safety

For newborns – when the temperature on the radiant warmer is beyond the normal range (36.5 to 37.5 deg Celsius), routine appropriate care as per neonatology department protocols will take precedence over the conduct of the experiment

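### Probe positions are neither fixed nor balanced across participants, so a consistent skin-site difference could not be told from a device bias

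*Protocol*

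**What the plan says.** Under Location of device & probes, the protocol states: "The RBM device will be placed on the abdomen between the xiphisternum and the umbilicus". The next sentence deals with the comparators: "Both the other probes (radiant warmer and the multichannel) will be placed near the RBM device separately". No side, distance, order or exchange of positions is given.

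Under Duration & frequency of sampling, the probes go on together: "Initially, after strapping on all 3 probes – there will be a waiting period of 10 minutes for temperature stabilization". No later repositioning is described, so each sensor appears to keep one spot for the whole session.

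Under Testing comparisons, the contrasts are "RBM device vs Radiant warmer probe vs Multichannel probe vs manual thermometer". No device is named as the reference and no agreement statistic is given. The sample is "25 mother-baby pairs", with "At least 5 readings from mother and 5 readings from a neonate".

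Under Device adhesion, covering is described for the tag only: "The RBM device will be strapped onto the abdomen using a combination of cotton and micropore adhesive tape".

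The SAP text was not available for this review.

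**The concern.** Three sensors cannot occupy the same patch of skin, so each difference between devices is also a difference between spots. If staff repeat one arrangement, device and spot coincide in every participant. The mean difference then estimates device bias plus the site effect. Readings every 5 minutes do not help, because a constant offset does not average out.

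The average difference between the tag and its comparators is an obvious result to take from a device comparison. A consistent site effect could create an apparent bias in a sound device or mask a real one. If the layout is fixed or goes unrecorded, this cannot be repaired once the data are in.

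**Working it through.** **The plan's own figure.** 25 pairs × (5 + 5) readings = 250, which agrees with the protocol as a count. The accompanying power statement cannot be checked uniquely, because no SD is given and the scale of the 5% is not defined. The present point does not depend on it.

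**Inputs.** From the protocol: 25 newborns (and 25 mothers), at least 5 readings each. Assumed, because the documents give no values: a constant site offset of 0.05 to 0.30 °C, a between-newborn SD of differences of 0.1 to 0.3 °C, and a within-participant SD of 0.1 °C for the simulation.

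**1. Where a site effect goes.** The mean paired difference was simulated for 25 participants with 5 readings each and a true device bias of zero.

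| Placement | Assumed site offset | Apparent device bias |
|---|---|---|
| Same layout every time | 0.05, 0.10, 0.20, 0.30 °C | 0.05, 0.10, 0.20, 0.30 °C |
| Balanced swap (24 participants) | same | about 0.00 °C |
| Haphazard, mean offset zero, placement SD 0.1 to 0.2 °C | 0 on average | 0.00 °C |

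In the haphazard case the cost is in precision. Compared with no placement variation, the SE of the mean difference rises from 0.009 to 0.022–0.041 °C, and the SD of differences from 0.100 to 0.141–0.222 °C.

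**2. Chance that a constant offset is declared a bias.** Take one mean difference per newborn, n = 25, and a two-sided 5% t-test against zero. The 95% CI half-width is t(0.975, 24) × SD/√25, with t = 2.064. The power is that of the noncentral t with noncentrality 5 × offset/SD.

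| Assumed SD | CI half-width | Offset 0.10 °C flagged |
|---|---|---|
| 0.1 °C | 2.064 × 0.1/5 = 0.041 °C | 99.8% |
| 0.2 °C | 2.064 × 0.2/5 = 0.083 °C | 67% |
| 0.3 °C | 2.064 × 0.3/5 = 0.124 °C | 36% |

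At SD 0.2 °C, offsets of 0.05 and 0.15 °C are flagged with probability 22% and 95%.

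**3. What a swap leaves.** Let b be the device bias and g the left-right offset. One layout has expected difference b + g and the other b − g. With odd and even numbers among 25 (13 and 12), the overall mean is b + g × (13 − 12)/25 = b + g/25. For g = 0.10 °C that leaves 0.004 °C. Fitting position removes even this, since the average of the two layout means is [(b + g) + (b − g)]/2 = b.

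**4. What a swap costs.** The offset moves into the spread unless position is fitted. With an offset of 0.20 °C and placement SD 0.1 °C, the simulated SD of differences is 0.141 °C with fixed positions and 0.248 °C after swapping without adjustment.

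**The case against.** **Only a consistent offset becomes bias.** A reader might infer that every skin-site difference turns into device bias. The protocol does not support that. It prescribes no layout, and placement that varies around zero mean offset leaves the mean difference unbiased. The concern depends on a habitual layout, which is plausible but not written down.

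**Reporting cannot be seen.** A reader might also infer that the study will report a site effect as device bias. The protocol names no bias statistic, and the SAP text was not available. What does stand is that no analysis could separate the two if the layout never varies, whatever the SAP says. Nor does the protocol call the tag's zone a reference site; it is simply the only zone defined.

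**The size is assumed.** Neither a gradient nor an SD is documented. The 67% figure belongs to one assumed SD and presumes a t-test that the protocol does not describe. Close placement already limits site differences. The only difference the protocol names is 5%; if that were 5% of an assumed 37 °C it would be 1.85 °C, whereas 0.10 °C is 0.27% of 37 °C. Against that, 0.10 °C is a tenth of the 1.0 °C normal range (36.5 to 37.5 °C) in the Participant safety section. Whether the true effect matters is open, and the design as written cannot show that it is negligible.

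**The swap is partial.** It protects RBM versus multichannel only. If the warmer probe's spot differed by 0.10 °C from both swapped positions, RBM versus warmer would keep the full 0.10 °C. The swap must also exchange whole spots: if one device always sat higher than the other, that difference would remain. These limits stand and are carried into the recommendation.

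**Covering is a different matter.** Cotton and tape travel with the tag, so swapping cannot isolate their effect, and strapping is arguably part of the device as used. The silence on how the comparators are covered should be treated as a separate point.

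**Conclusion.** The concern holds in conditional form. The protocol leaves the comparators' positions open and does not balance them. Under a habitual layout, a consistent skin-site offset passes one-for-one into the mean difference between devices and cannot be recovered by analysis. Under haphazard placement the result is wider spread, not bias.

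The size is unknown. The probabilities of about 100%, 67% and 36% for a 0.10 °C offset rest on an assumed offset, assumed SDs of 0.1, 0.2 and 0.3 °C, and a t-test on 25 newborn means. They show that a modest offset could matter, not that one exists. This does not make the study invalid. It is a weakness that is cheap to remove before data collection and cannot be removed afterwards. A change is advisable.

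**What to change.** Under Location of device & probes, add:

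- Within the stated abdominal zone, define a left and a right position. Odd participant numbers have the RBM tag on the left and the multichannel probe on the right; even numbers have the reverse. Apply this separately to mothers and newborns.
- Keep the radiant warmer probe near the tag, as the protocol already says.
- Record the layout of all three probes for each participant.

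In the analysis, include position for both the mean difference and the limits of agreement. State in the report that RBM versus warmer may still include a site effect. Deal with the covering of the probes in its own instruction, since the swap does not touch it.

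The cost is a short addition to the protocol, one data field and a layout card for staff to follow, with no extra participants or session time. The statistical downside is that limits of agreement calculated without the position term may widen.

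### The 80% power is attached to 250 readings, which are repeats on 50 people, and cannot be reproduced from the protocol text

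*Protocol*

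**What the plan says.** The protocol's section on sample size and sampling technique sets the sample at "25 mother-baby pairs" and at 250 readings, noting "At least 5 readings from mother and 5 readings from a neonate". It adds that "A sample size of about 250 readings will ensure a power of 80% to detect a 5% difference in measurements between devices", with 95% confidence.

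The section on testing comparisons lists four instruments: the RBM device, the radiant warmer probe, the multichannel probe and a manual thermometer. The section on duration and frequency of sampling has readings from the three automatic devices every 5 minutes. For the fourth instrument it says "Manual thermometer readings will be taken every 15 minutes at the following 5 timings: 0, 15, 30, 45 and 60 minutes".

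The only temperature range given is under participant safety, where newborn care takes precedence if the warmer reading is "beyond the normal range (36.5 to 37.5 deg Celsius").

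The supplied protocol text gives no SD of the between-device difference, no baseline proportion, no scale for the 5%, no test or sidedness, no named pairwise comparison and no within-person correlation. The SAP text was removed before review, so these gaps are shown for the protocol only.

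**The concern.** Readings taken on one person within an hour share that person's skin, probe placement and device fit. If one device reads high against another on a given person, it may well do so at all five times. Repeats then carry less information than the same number of readings on different people, and a power figure per reading describes a different design from 25 pairs measured repeatedly.

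The effect size is also undefined. Five per cent of a Celsius temperature, five percentage points of agreement and five per cent of some other quantity lead to very different calculations. Without the scale and the SD, a reader of the protocol cannot tell what difference in deg C the study can detect or how precisely it will estimate one. Device comparison is the testing that the protocol describes, so this sentence is its main justification for the sample size.

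**Working it through.** **Inputs from the protocol.** 25 pairs; at least 5 readings per mother and per neonate; about 250 readings; 80% power; 95% confidence, taken here as two-sided alpha 0.05; normal range 36.5 to 37.5 deg C.

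**Inputs assumed.** The intraclass correlation (ICC) of between-device differences within a person, over a range. Comparisons are treated as paired and normal approximations are used. Except where stated, the 50 people are treated as independent, ignoring correlation between mother and baby.

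**1. The count reproduces.** 25 × 2 × 5 = 250.

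**2. The 80% does not.** For paired differences, n = (SD × (1.960 + 0.842) / difference)². With n = 250 independent differences, 80% power corresponds to 2.802 / √250 = 0.177 SD. The supplied text has nothing to convert this to deg C.

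**3. If 5% means 5% of temperature.**
- The range midpoint is (36.5 + 37.5)/2 = 37.0, and 5% of it is 1.85 deg C (1.825 to 1.875 across the range). The whole range is 1.0 deg C wide.
- Implied SD of differences: 1.85 / 0.1772 = 10.4 deg C (10.3 to 10.6). A two-sample calculation would imply 7.4 deg C with 250 per group, or 5.2 with 125 per group.
- With 50 independent units, power is at least 80% for any SD up to 1.85 × √50 / 2.802 = 4.67 deg C. With 25 units the limit is 1.85 × √25 / 2.802 = 3.30. Noncentral t gives 4.58 and 3.17.

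**4. If the 80% was computed for 250 independent paired readings at the true SD.** The effect is 0.177 SD. With m matched readings per person, the design effect is 1 + (m − 1) × ICC, effective n = 50m / design effect, and power = Φ(0.1772 × √(effective n) − 1.960). Detectable difference (80% power) = 2.802 / √(effective n). The 95% CI half-width = 1.960 / √(effective n).

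Comparisons with the manual thermometer have m = 5. Comparisons among the three automatic devices could have m = 13, assuming 0 to 60 minutes inclusive (60/5 + 1 = 13; 13 × 50 = 650 readings).

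| ICC (assumed) | Effective n, m = 5 | Power, m = 5 | Detectable difference, m = 5 | CI half-width, m = 5 | Effective n, m = 13 | Power, m = 13 |
|---|---|---|---|---|---|---|
| 0 | 250 | 80% | 0.177 SD | 0.124 SD | – | – |
| 0.1 | 178.6 | 66% | 0.210 SD | 0.147 SD | 295.5 | 86% |
| 0.2 | 138.9 | 55% | 0.238 SD | 0.166 SD | 191.2 | 69% |
| 0.5 | 83.3 | 37% | 0.307 SD | 0.215 SD | 92.9 | 40% |
| 0.8 | 59.5 | 28% | 0.363 SD | 0.254 SD | 61.3 | 28% |

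- With m = 13, effective n stays at 250 or more while 1 + 12 × ICC ≤ 650/250 = 2.6, that is, up to an ICC of 1.6/12 = 0.13.
- However many readings are taken, effective n cannot exceed 50/ICC. At ICC 0.20 that limit is 250, so above it no number of readings restores 80% for this effect.
- Mother-baby correlation would lower these figures further. With a common ICC of 0.5 over all 10 readings in a pair, effective n is 250/5.5 = 45.5 and power is 22%.

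**5. If 5% means five percentage points.** Some assumed inputs land near 250: 0.94 versus 0.99, two-sided with continuity correction, needs 250 per group, and a McNemar test with 8% discordance needs 249. None of these inputs is in the protocol, and these calculations also treat readings as independent.

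**The case against.** The strongest reply is that the SAP was removed before review and may define the difference, the SD and the clustering. That stands: the gaps are established only for the protocol text. It does not change the protocol sentence, which attaches power to readings.

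Second, the protocol asks for at least five readings, so 250 is a minimum. Among the automatic devices, 13 matched readings per person would keep power at or above 80% up to an ICC of about 0.13. This also stands, so the claim that 80% is too high must be limited to five matched readings per person. The manual thermometer has only five scheduled times, so that case covers every comparison with it.

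Third, the ICCs are assumed, and what matters is correlation of the between-device differences, not of raw temperatures. The documents give no value, so the reduced powers are illustrations. The 36.5 to 37.5 deg C range is likewise a newborn care threshold on the warmer, not a range of device differences and not stated for mothers. It serves here only as a rough yardstick.

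A reader might go further and infer that the study is underpowered. The documents do not support that. If 5% means 1.85 deg C, even 50 independent units give at least 80% power for any SD up to 4.67 deg C. Nor can it be said that the 80% is wrong on every reading, because the proportion scale cannot be excluded.

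**Conclusion.** The point holds as one about the unit and the missing inputs. The protocol attaches 80% power to about 250 readings that are at least five repeats on each of 50 people in 25 pairs, and the supplied text does not allow the figure to be reproduced.

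The consequence depends on what was meant. If the 80% assumed 250 independent paired readings, it is overstated for five matched readings per person under any positive within-person correlation, falling to between 66% and 28% over assumed ICCs of 0.1 to 0.8. If 5% means 5% of temperature, the power sentence does not describe this design and says nothing about smaller, more relevant differences. If it means percentage points, its inputs are missing too. Whether the sample is adequate cannot be judged until the inputs are stated. This should be fixed; it is not evidence that the trial is too small.

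**What to change.** In the protocol's sample-size section:

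- State the sample as 50 participants in 25 mother-baby pairs with repeated readings.
- Name the device comparison that is powered, its test and its sidedness.
- Give the target difference in deg C (or define the proportion scale and baseline) and the assumed SD of the between-device difference.
- Replace the per-reading power statement with power, or 95% CI half-width, based on participant means, or on the design effect 1 + (m − 1) × ICC over a stated ICC range, giving the number of matched readings m for that comparison.

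If the SAP does not already do so, analyse between-device differences with participant- and pair-level random effects, or with cluster-robust intervals.

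The cost is a reworded paragraph, a few stated inputs and a little more analysis work. The stated power may come out less favourable. Restating it needs no change in enrolment.
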